#### 11.2 SAMPLE SIZE DETERMINATION

Sample size was calculated using formulas based on normal approximation to the binomial distribution. Previously recorded historical biopsy results for Melanoma, Squamous cell carcinoma, and Basal cell carcinoma across the proposed Study Sites averaged 2.3%, 12.5% and 29.2% of in-person dermatology Provider visits (i.e. cases), respectively. This represents disease prevalence rates in this pivotal Study target population of interest (i.e. patients who visited a Study Site within a 365 day period specifically for a mole spot check with concern for skin cancer, or a full body skin exam (FBSE) for the purpose of skin cancer prevention. This calculation presumes the exclusion of all other dermatology visits not related to a concern for skin cancer. Formulae (1) and (2) were used to estimate the sample size needed to evaluate the sensitivity (Se) and specificity (Sp), based on the diagnostic performance data available for melanoma from the SMSA Performance Study, and the target population case prevalence rates. The following values are inserted:  $Z_{\alpha/2} = 1.96$  for  $\alpha = 0.05$  level of significance, and  $d = 10\%$  margin of error for 95% Confidence Interval.

$$n_{Se} = \frac{Z_{\frac{\alpha}{2}}^2 \widehat{Se} (1 - \widehat{Se})}{d^2 \times \text{Prev}} \quad (1)$$

$$n_{Sp} = \frac{Z_{\frac{\alpha}{2}}^2 \widehat{Sp} (1 - \widehat{Sp})}{d^2 \times (1 - \text{Prev})} \quad (2)$$

Table 4 and Table 5 below summarizes the sample size estimates for cutaneous diseases of interest to evaluate the sensitivity and specificity of the investigational device (Sklip System). As can be seen from the table, the size estimate calculated using the sensitivity value for detecting melanoma (423 cases [lesions]) yields the largest number. The expected numbers of lesions that will be accordingly captured during the Study are summarized in Table 6.

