Considering the larger number of cases required for evaluation of sensitivity (423 for Melanoma; based on SMSA performance of sensitivity for melanoma of 97.4%) as opposed to specificity (114 for SCC), a 49% specificity can be estimated from the hypothetical sample data. Previous peer-reviewed studies, exclusive to virtual visits, showed that participants submitted an average of 1.02 to 1.9 images per participant. Considering the aforementioned and average case submission rates reported by the proposed Study Sites, we expect a case submission rate of 1.5 per Study Participant. Assuming a 10% drop-out rate a total number of 310 Participants (dropout-inflated sample size) will be needed for the current study (310 = 423 ÷ 1.5 × 1.10).

**Table 4. Sample size estimates for cutaneous diseases of interest to evaluate the sensitivity of Sklip System based on the available target population prevalence data.**

Lesions	Sample Size Estimate to Test for Sensitivity											
	Melanoma			BCC			SCC			AMN		
	Confirmed	Excluded	Total	Confirmed	Excluded	Total	Confirmed	Excluded	Total	Confirmed	Excluded	Total
Suspicious	9	248	257	17	89	107	17	31	48	17	243	260
Non-Suspicious	1	165	166	1	38	39	1	13	14	1	104	105
Total Scanned	10	413	423	18	128	146	18	44	63	18	347	365
Prevalence	2.3%			12.5%			29.2%			5.0%		
Sensitivity	97.4%			95%			95%			95%		
Specificity	40%			30%			30%			30%		

The sample size was estimated using formulae (1) and (2) to test for sensitivity and specificity, respectively, with  $\alpha = 0.05$  significance level and 10% margin of error for 95% Confidence Interval. The respective sensitivity and specificity values were used to estimate the numbers of suspicious and non-suspicious lesions confirmed or excluded by the Ground Truth as described in the Sections above. BCC: Basal cell carcinoma, SCC: Squamous cell carcinoma, AMN: Atypical melanocytic nevi with uncertain malignant potential.

**Table 5.** Sample size estimates for cutaneous diseases of interest to evaluate the specificity of Sklip System based on the available target population prevalence data.

Sample Size Estimate to Test for Specificity											
Melanoma			BCC			SCC			AMN		
Confirmed	Excluded	Total	Confirmed	Excluded	Total	Confirmed	Excluded	Total	Confirmed	Excluded	Total
2	55	57	11	56	67	32	56	88	4	56	61
0	37	37	1	24	25	2	24	26	0	24	24
2	92	94	12	81	92	33	81	114	4	81	85
2.3%			12.5%			29.2%			5.0%		

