#### 11.4.2 ANALYSIS OF PRIMARY ENDPOINT(S)

For the Primary Endpoints, the SMSA outputs of “SUSPICIOUS” or “UNREMARKABLE” from Participant-taken DDI will be compared to the Ground Truth, described in the Sections above. For **Melanoma and atypical melanocytic nevi with uncertain malignant potential** (moderate, severe, and high grade atypia; those with pathology reports that include notes such as: borderline, cannot exclude melanoma, cannot exclude early evolving melanoma, unusual features, atypical spitz nevi, suspicion for melanoma, re-excision (or further removal) should be considered or is recommended in the pathologist management comment), a 2x2 table consisting of the following counts (number of PSLCs):

- True Positives (TP): the SMSA output of SUSPICIOUS agrees with the Ground Truth for PSLCs that were

biopsied and were diagnosed as Melanoma or atypical melanocytic nevi with uncertain malignant potential, using Dataset (O) (Histologic diagnosis ground truth (H-GT)),

- False Positives (FP): the SMSA output of SUSPICIOUS does not agree with the benign Ground Truth using Dataset (N) (DDI dermoscopic diagnosis ground truth) and Dataset (O)
- False Negatives (FN): the SMSA output of UNREMARKABLE does not agree with the Ground Truth for PSLCs that were biopsied and diagnosed as Melanoma or atypical melanocytic nevi with uncertain malignant potential using Dataset (O)
- True Negatives (TN): the SMSA output of UNREMARKABLE agrees with the benign Ground Truth, using both Dataset (N) and Dataset (O)

For **Melanoma and atypical melanocytic nevi with uncertain malignant potential**, Sensitivity ( $TP \div (TP + FN)$ ) of the Sklip System will be calculated with a lower one-sided 95% confidence interval using the Exact (Clopper-Pearson) method. For **Squamous cell carcinoma** and for **Basal cell carcinoma**, Sensitivity and lower one-sided confidence intervals will be estimated in the same manner as for Melanoma and atypical melanocytic nevi with uncertain malignant potential.

Specificity ( $TN \div (FP + TN)$ ) will be the same for Melanoma and atypical melanocytic nevi with uncertain malignant potential, SCC, and BCC, where:

- False Positives (FP): the SMSA output of SUSPICIOUS does not agree with the benign Ground Truth, using Dataset (N) and Dataset (O)
- True Negatives (TN): the SMSA output of UNREMARKABLE agrees with the benign Ground Truth, using Dataset (N) and Dataset (O)

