Specificity will be estimated with a lower one-sided 95% confidence interval using the Exact (Clopper-Pearson) method. Two-sided 95% confidence intervals for all Sensitivities and Specificities will also be calculated using the Exact (Clopper-Pearson) method.

We also will estimate the following measures of triage accuracy for each cutaneous disease entity with two-sided 95% confidence intervals using the Exact (Clopper-Pearson) method :

- $Accuracy (P) = (TP + TN) \div (TP + FP + FN + TN)$
- $Positive predictive value (PPV) = TP \div (TP + FP)$
- $Negative predictive value (NPV) = TN \div (FN + TN)$
- $Prevalence = (TP + FN) \div (TP + FP + FN + TN)$

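### Section 11.4.2 calculates each entity's prevalence and PPV against benign lesions only and does not label them so (melanoma-group prevalence 12.4% where Table 6 plans 7.3%); a separate minor gap is that no method is named for several lesions from one participant

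*Combined protocol and SAP*

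**What the plan says.** **Cells.** Section 11.4.2 sets out, for the melanoma group (melanoma plus atypical melanocytic nevi with uncertain malignant potential, AMN), "a 2x2 table consisting of the following counts (number of PSLCs". True positives and false negatives are biopsied lesions with that histologic diagnosis. A false positive is a lesion for which "the SMSA output of SUSPICIOUS does not agree with the benign Ground Truth using Dataset (N" or Dataset (O); true negatives are likewise confined to benign lesions. SCC and BCC sensitivity follow the same pattern. Specificity "will be the same for Melanoma and atypical melanocytic nevi with uncertain malignant potential, SCC, and BCC, where" one shared benign group supplies both counts.

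**Measures.** The section continues: "We also will estimate the following measures of triage accuracy for each cutaneous disease entity with two-sided 95% confidence intervals". It prints formulas for accuracy, PPV, NPV and prevalence from the four cells. Prevalence is (TP + FN) ÷ (TP + FP + FN + TN). The primary endpoint row in section 2.1 lists PPV, NPV and accuracy, but not prevalence.

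**Planned prevalence.** Section 11.2 reports that historical biopsy results for "Melanoma, Squamous cell carcinoma, and Basal cell carcinoma across the proposed Study Sites averaged 2.3%, 12.5% and 29.2" per cent of visits, and adds: "This represents disease prevalence rates in this pivotal Study target population of interest". Table 6 applies its prevalence row to all 423 lesions.

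**Lesions per participant.** Section 11.2 states: "we expect a case submission rate of 1.5 per Study Participant". Sections 11.4.2 and 11.4.3 specify Clopper-Pearson intervals and McNemar tests. Section 11.4.1 says that assumptions will be checked and alternatives considered, but names neither clustering nor a method.

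**The concern.** The word prevalence carries two meanings in one plan. In section 11.2 and Table 6 it is a share of all cases or lesions. In section 11.4.2 its denominator omits every lesion of the other target cancers. A sample that matched Table 6 exactly would report a higher prevalence than Table 6 shows.

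PPV has the same feature, and it belongs to the primary endpoint row. An unlabelled PPV for the melanoma group will be read as the chance that a lesion flagged SUSPICIOUS is a melanoma or atypical nevus. The formula answers a different question, because flagged BCC and SCC lesions are removed first.

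A second, independent matter is that lesions from one participant may be correlated. If that correlation is positive, intervals and tests that assume independent lesions are slightly too optimistic.

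**Working it through.** **Inputs (Table 6, section 11.2)**

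| | Melanoma | AMN | BCC | SCC | Negative | Printed total |
|---|---|---|---|---|---|---|
| Suspicious | 9 | 14 | 36 | 84 | 113 | 257 |
| Non-suspicious | 0 | 6 | 15 | 36 | 107 | 166 |
| Total | 10 | 21 | 52 | 121 | 220 | 423 |

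The cells do not add exactly to the printed totals because of rounding, so results are given on both bases where they differ.

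**1. The plan's own figures.** Formula (1): 1.96² × 0.974 × 0.026 ÷ (0.10² × 0.023) = 423.0 lesions. Participants: 423 ÷ 1.5 × 1.10 = 310.2, stated as 310. Melanoma-group prevalence: 2.3% + 5.0% = 7.3%, which is (10 + 21)/423. Section 11.2 also says that "a 49% specificity can be estimated from the hypothetical sample data"; 107/220 = 48.6%, so the planning text uses the benign-only comparator too.

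**2. Prevalence by the section 11.4.2 formula**

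| Entity (table labels) | Total row: formula | Total row: all lesions | Cells: formula | Cells: all lesions |
|---|---|---|---|---|
| Melanoma group | 31/251 = 12.4% | 31/423 = 7.3% | 29/249 = 11.6% | 29/423 = 6.9% |
| BCC | 52/272 = 19.1% | 52/423 = 12.3% | 51/271 = 18.8% | 51/423 = 12.1% |
| SCC | 121/341 = 35.5% | 121/423 = 28.6% | 120/340 = 35.3% | 120/423 = 28.4% |

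On the Total row the ratios are 1.7, 1.6 and 1.2. Device performance does not enter, because TP + FN and FP + TN are fixed by the ground truth. The section 11.2 text gives 12.5% to SCC and 29.2% to BCC, while Tables 4 to 6 give the reverse. Swapping them exchanges the last two rows and leaves the melanoma group unchanged, but the passages should be reconciled.

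**3. PPV on the Table 6 cells**

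- Melanoma group: 23/(23 + 113) = 16.9%, against 23/257 = 8.9% of all SUSPICIOUS outputs.
- BCC: 36/149 = 24.2% against 36/257 = 14.0%.
- SCC: 84/197 = 42.6% against 84/257 = 32.7%.

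**4. PPV with Table 4 sensitivities.** Melanoma-group TP = 10 × 0.974 + 21 × 0.95 = 29.7. FP = 220 × 0.70 = 154 at 30% specificity, or 220 × 0.60 = 132 at 40%. Other targets flagged = 173 × 0.95 = 164.

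- Versus benign: 29.7/183.7 = 16.2% to 29.7/161.7 = 18.4%.
- Of all SUSPICIOUS: 29.7/348.0 = 8.5% to 29.7/326.0 = 9.1%.

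The roughly twofold gap does not depend on how Table 6 splits its cells.

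**5. Clustering.** The documents give no intraclass correlation (ICC), so 0.1 to 0.5 is an assumption. Design effect = 1 + (1.5 − 1) × ICC = 1.05 to 1.25, and its square root is 1.02 to 1.12. One-sided 95% Clopper-Pearson bounds, with count and denominator divided by the design effect:

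| | Bound, design effect 1 | Bound, design effect 1.25 | Goal | Smallest count meeting the goal, 1 → 1.25 |
|---|---|---|---|---|
| Specificity, 107/220 | 42.9% | 42.2% | 30% | 78 → 80 of 220 |
| BCC at 95%, n = 52 | 86.8% | 85.4% | 80% | 47 → 48 |
| SCC at 95%, n = 121 | 90.4% | 89.7% | 80% | 105 → 106 |

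Using 1.5 for every denominator overstates the effect for BCC and SCC. With 423/1.5 = 282 participants, BCC averages 52/282 = 0.18 lesions per participant, SCC 121/282 = 0.43 and benign 220/282 = 0.78. In the other direction, uneven numbers per participant raise a design effect. At 1.9 lesions, the upper end of the range that section 11.2 cites, and ICC 0.5, it is 1.45 and the counts become 81, 48 and 106.

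**The case against.** **Nothing is undefined.** Section 11.4.2 writes out all four cells, restricts false positives and true negatives to benign lesions, and prints every formula. An analyst could produce only one set of numbers. This stands. What is missing is a statement that the other targets leave the denominators, and that this prevalence is not the one in section 11.2.

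**No goal depends on it.** Sensitivity, specificity and their goals are untouched, and no passage commits to comparing observed prevalence with Table 6. This also stands, and it limits the weight of the point. A reader might infer that the benign-only comparator is itself an error. The documents do not support that: it is a reasonable comparator for a triage device, it fits the common specificity, and section 11.2 uses it.

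**Table 6 cells are a weak basis for some figures.** They imply sensitivities of 36/52 = 69% for BCC, 84/121 = 69% for SCC and 14/21 = 67% for AMN, where Table 4 assumes 95%. A reader might infer from the cells an any-target NPV of only 107/166 = 64.5%. That is not supported. With Table 4 sensitivities the missed targets are 10 × 0.026 + 194 × 0.05 = 9.96, and NPV is 66/75.96 = 87% at 30% specificity or 88/97.96 = 90% at 40%. Adding up the three prevalences or the three PPVs would also show nothing, because their denominators differ.

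**Clustering is small.** Agreed. The commitment in section 11.4.1 to consider alternatives does not name a method, but the expected effect is slight.

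**Conclusion.** The point holds as a minor one. Followed as written, section 11.4.2 gives a melanoma-group prevalence of 12.4% where the same lesions give the planned 7.3% (Total row), or 11.6% against 6.9% (cells). It gives a PPV about twice the share of SUSPICIOUS outputs that are melanoma or atypical nevus. The prevalence result rests only on the Table 6 composition; the PPV result holds under both the Table 6 cells and the Table 4 sensitivities.

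The missing cluster method is a separate and smaller gap. At 1.5 lesions per participant and an assumed ICC of 0.1 to 0.5, the standard error rises by at most about 2% to 12%, less for BCC and SCC. The count needed to meet a goal moves by at most 2 lesions. A reader might infer that clustering puts the primary conclusions in doubt; at the planning values none changes, and it could matter only for a result very close to a goal.

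**What to change.** **Prevalence and predictive values**

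- Compute entity prevalence as entity lesions divided by all PSLCs with a binary output.
- Report the entity share of all SUSPICIOUS outputs.
- Add any-target PPV and NPV. Because these denominators include all analysed lesions, state how an unbiopsied lesion with a target image-based ground truth is counted.
- Label any retained entity PPV, NPV and accuracy as entity versus benign, other targets excluded. Entity accuracy should not be recast over all lesions, since a correctly flagged SCC would then count as an error in the melanoma table.

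**Clustering**

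- For specificity and the SCC and BCC bounds, name a participant-clustered interval: a cluster bootstrap, or Clopper-Pearson adjusted by a design effect based on the observed lesions per participant in that denominator.
- For exploratory endpoints 1 and 2, name a clustered McNemar test.

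**Cost.** SAP wording and standard code; no new data. Reported prevalence becomes lower (melanoma group 12.4% to 7.3% on the Total row), the entity share is lower than the versus-benign PPV (8.9% against 16.9% on the cells), and intervals become slightly wider. Retained entity NPV and accuracy keep their values and gain a label.

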#### 11.4.3 ANALYSIS OF THE EXPLORATORY ENDPOINTS

##### *Exploratory endpoint 1*

Similar to the Primary endpoint, the accuracy of SMSA output using Participant-taken DDI will be assessed using a 2x2 table, where the SMSA output of “SUSPICIOUS” or “UNREMARKABLE” will be compared to the SMSA output using Study Coordinator-taken DDI (near-perfect technical quality), simulating a laboratory-type environment where the SMSA is fed the near-perfect technical quality DDI.

The Sensitivity of the SMSA output from Participant-taken DDI will be compared to the Sensitivity of the SMSA output from Study Coordinator-taken DDI using McNemar’s Test, given the paired nature of the data, using 0.05 significance level.

The Specificity of the SMSA output from Participant-taken DDI will be compared to the Specificity of the SMSA output from Study Coordinator-taken DDI using McNemar’s Test, given the paired nature of the data, using 0.05 significance level.

This will be done for each disease entity:

- Melanoma and atypical melanocytic nevi with uncertain malignant potential,
- Squamous cell carcinoma,
- Basal cell carcinoma

#### *Exploratory endpoint 2*

Using only PSLs < 6 mm in diameter, the accuracy of the expert consensus triage decision using Participant-taken smartphone clinical images (SCI) will be assessed using a 2x2 table, where the expert consensus triage decision of “BIOPSY” or “MONITOR” will be compared to the intervention method, for both SMSA outputs recorded by Participants and SMSA outputs recorded by Study Coordinators for the same target PSLCs.

The Sensitivity of the SMSA output will be compared to the Sensitivity of the expert consensus triage decision of Participant-taken SCI using McNemar’s Test, given the paired nature of the data (i.e. the same PSLCs < 6mm), using 0.05 significance level.

The Specificity of the SMSA output will be compared to the Specificity of the expert consensus triage decision of Participant-taken SCI using McNemar’s Test using 0.05 significance level.

Estimates with two-sided 95% confidence intervals will be calculated using the Exact (Clopper-Pearson) method.

This will be done for each disease entity:

- Melanoma and atypical melanocytic nevi with uncertain malignant potential,
- Squamous cell carcinoma,
- Basal cell carcinoma

#### *Exploratory endpoint 3*

Using only Melanomas < 0.8 mm Breslow depth, the accuracy of the expert consensus triage decision using Participant-taken smartphone clinical images (SCI) will be assessed using a 2x2 table, where the expert consensus triage decision of “BIOPSY” or “MONITOR” will be compared to the intervention method, for both SMSA outputs recorded by Participants and SMSA outputs recorded by Study Coordinators for the same target PSLCs.

The Sensitivity of the SMSA output will be compared to the Sensitivity of the expert consensus triage decision of Participant-taken SCI using McNemar’s Test, given the paired nature of the data (i.e. the thin melanomas < 0.8 mm Breslow depth), using 0.05 significance level.

Estimates with two-sided 95% confidence intervals will be calculated using the Exact (Clopper-Pearson) method.

#### *Exploratory endpoint 4*

We will calculate the following based on Participant self-skin exams (SSEs) performed during the At-home Phase:

- (a) the mean and standard deviation of the number of PSLCs identified by Participants performing a SSE, and
- (b) the mean and standard deviation of the number of PSLCs identified by the dermatology Provider during the In-person Phase full body skin exam (FBSE).

The mean difference and 95% confidence interval will be calculated and assessed by paired t-test.

